9.2 NON-CONSTANT VARIANCE & ASSESSMENT OF SITE HOMOGENEITY

A generative model will be fit of the following form:

$$\begin{aligned} \text{Score Difference} &\sim N(\mu, \sigma) \\ \mu &= \alpha\mu + \beta_1 * \text{Location} + \beta_2 * \text{Test Order} \\ \sigma &= k * \exp(\alpha\sigma + \beta_3 * \text{Average Score}_2 + \beta_4 * \text{Average Score}) \end{aligned}$$

- ‘Location’ and ‘Test Order’ will be one hot encoded indicator variables for the trial location site and order in which the test was given (ie. DCTclock pen assessment first or DCTclock tablet assessment first) respectively.
- Average Score will be calculated as: $(\text{DCTclock pen score} + \text{DCTclock tablet score}) / 2$
- Score Difference will be calculated as: $(\text{DCTclock tablet score} - \text{DCTclock pen score})$
- The parameters k , $\alpha\mu$, and $\alpha\sigma$ are constants

This model will permit the disentangling of site specific impacts and the rate of learning improvement between the first and second assessments while also allowing the variance in score difference to vary as a function of the average score.

The Evaluable Population will be used for this analysis.

Two tables will summarize this model. The first will include the mean estimated coefficient values along with their 96% credible intervals. The second will breakdown the estimated differences in average Score Difference between the site locations and the order in which the assessments were completed. This table will include the mean differences as well as the max 96% prediction interval ranges for each combination of site and order.

A figure will display the 96% prediction intervals for Score Difference (y-axis) as a function Average Score (x-axis) over the range 0 - 100 generated from the fit model above. The Evaluable Population will be plotted over this interval for a visual assessment of the model fit. The max 96% prediction interval range will be added to the figure.

9.3 SECONDARY EFFECTIVENESS VARIABLES AND ANALYSES

In addition to the above primary analysis, the following additional agreement analyses between DCTclock-tablet and DCTclock-pen scores will be conducted on the DCTclock overall score as well as the scores from each of the Composite Scales (Drawing Efficiency, Information Processing, Simple and Complex Motor, and Spatial Reasoning) unless otherwise specified:

- Perform the Bland-Altman analysis on the scores from the composite scales; however, there will be no formal equivalence testing for the composite scales.
- DCTclock-tablet scores will be plotted against DCTclock-pen scores in a scatter plot, superimposed with a line of identity.
- An unweighted Deming regression (where the variance of the measurement error for each of DCTclock-pen and DCTclock-tablet is determined by the two measurements that were collected 3-5 weeks apart) will be carried out to determine the y-intercept, slope and their two-sided 95% CIs.
- The intraclass correlation coefficient (ICC) between DCTclock-table and DCTclock-pen will be calculated and will be placed on the above-mentioned plot of tablet vs. pen score scatter plot.

- Root mean squared differences (RMSD), the square root of the average squared discrepancy score, will be calculated to indicate the average amount by which scores differ. RMSD will be calculated using the following formula:

$$RMSD = \sqrt{\frac{\sum_{i=1}^N (x_{1,i} - x_{2,i})^2}{N}}$$

where $x_{1,i}$ is the DCTclock-pen score for subject i , $x_{2,i}$ is the DCTclock-tablet score for subject i , and where N is the sample size.

- Mean differences will be compared between pen and tablet using paired t-tests for equivalence, where lower and upper equivalence limits are -30 and 30, respectively. The following is the hypothesis test for equivalence. This hypothesis testing will be done only for the DCTclock Overall Score.

$H_0: \mu_d \leq -30 \text{ or } \mu_d \geq 30$

$H_1: -30 < \mu_d < 30$

where μ_d is the true average difference of the pen minus tablet total scores.

The Evaluable Population will be used for these analyses.

Tables will summarize the secondary effectiveness endpoints. These tables will include descriptive statistics for the DCTclock-pen score, for the DCTclock-tablet score, for the difference between the DCTclock-pen score and the DCTclock-tablet score (calculated as tablet minus pen), upper and lower LoA and their respective CIs, and RMSD. These statistics will be generated by randomization group and overall. One table will be created for each of the DCTclock composite scale scores.

Figures will display the plots described above.

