### 4 STUDY DESIGN AND ENDPOINTS

#### 4.1 DESCRIPTION OF THE STUDY DESIGN

This study is a randomized crossover trial consisting of two test visits separated by a washout period of 3 to 5 weeks. Subjects are randomized into two equal groups. Group 1 receives DCTclock-pen at the first visit, with the DCTclock-tablet given at the second visit; Group 2 receives DCTclock-tablet at the first visit, followed by DCTclock-pen at the second visit. At Visit 1 (day 0), eligibility is assessed and a version of the DCTclock test is administered based on the group allocation. A battery of Linus Platform tests and reference standard tests are also administered. At visit 2 (day 21-35), eligibility is assessed and the alternate version of the DCTclock test is administered based on the group allocation. A battery of Linus Platform tests is also administered, together with reference standard tests. Equivalence of DCTclock-pen and DCTclock-tablet will be tested. Linus Platform test data will be collected to develop novel measures of cognitive and motor function and assess their accuracy in detecting impairment, construct validity, and test-retest reliability. 200 subjects will be recruited to participate with the anticipation that 175 will be available for analysis.

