### 7.3.2 VISIT 2 (FINAL STUDY VISIT)

#### Visit 2 (Day 21-35) ~ 94 minutes total

Visit 2 Screening (2 mins)	Time Estimate
Assessment of impairment of the dominant hand	1 min

Assessment of recreational drug or alcohol use/change in medications	1 min
--	-------

If a subject screen fails at any step, they will not complete the remaining assessments; eligible subjects will complete the following study assessments.

Visit 2 Study Assessments (92 mins)	Time Estimate
Alternate version of DCTclock from visit 1 (if DCTclock-pen version was administered, then DCTclock-tablet version is to be administered and vice versa based on randomization group allocation)	5 mins
Linus Platform drawing tests with list learning	15 mins
Linus Platform decision making and reaction time assessments with PHQ-9	10 min
Linus Platform lifestyle questionnaire	10 min
Linus Platform speech elicitation tasks	10 min
Linus Platform eye tracking-based memory assessment	5 mins
Linus Platform gait and balance assessment	5 mins
RBANS	30 min
Linus Platform reaction time assessment	2 mins

This visit ends the participant's participation in this study.

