## 7.3.4 SCHEDULE OF EVENTS TABLE

Procedure	Screening/Visit 1	Visit 2
Time	Day 0	Within 3-5 weeks of visit 1
Consent	X	
Inclusion/Exclusion Criteria	X	X
Medical History/Demographics	X	
MMSE	X*	
Hamilton-Veale Contrast Sensitivity	X	
Purdue Peg Board	X	
Brief Neurological Assessment	X	
DCTclock Test (either digital pen or tablet version)	X	X
Linus Platform drawing tests	X	X
Linus Platform decision making and reaction time assessments	X	X^ &
Linus Platform lifestyle questionnaire		X
Linus Platform gait and balance assessment	X	X
RBANS	X	X
Linus Platform speech elicitation assessments	X#	X
Linus Platform eye tracking-based memory assessments		X
Assessment of adverse device effects	X	X

\*- MMSE not administered if a LAR consents to the study due to a documented prior MMSE or MoCA score of  $\leq 18$

 PHQ-9 depression screen is included in the decision making and reaction time assessments on visit 2 only

^ reaction time only is assessed twice on visit 2

#- List learning only is combined with the drawing tests on visit 1. All speech and voice assessments are given on visit 2.

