- An unweighted Deming regression (where the variance of the measurement error for each of DCTclock-pen and DCTclock-tablet is determined by the two measurements that were collected 3-5 weeks apart) will be carried out to determine the y-intercept, slope and their two-sided 95% confidence intervals.
- The intraclass correlation coefficient (ICC) will be calculated
- Root mean squared differences (RMSD), the square root of the average squared discrepancy score, will be calculated to indicate the average amount by which scores differ.
- Mean differences will be compared using paired t-tests for equivalence, where lower and upper equivalence limits are -30 and 30, respectively.

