3.2.3 EXPLORATORY ENDPOINTS

Linus Platform individual tests will be compared to Mini-Mental State Exam (MMSE) and Repeatable Battery for the Assessment of Neuropsychological Status (RBANS) to measure agreement in assessment of cognitive status in the evaluable dataset. The list of Linus platform individual tests are as follows:

- Linus Platform drawing tests
 - Pre-test
 - Pathfinding test
 - Symbol test
 - Connect test
 - Tracing test
- Linus Platform decision making and reaction time tests
 - Simple reaction time
 - Procedural reaction time
 - Go/No-go
 - PHQ-9
- Linus Platform speech elicitation tasks
 - Complex picture description
 - Category naming
 - Object recall
 - Sentence reading
 - Sustained phonation
 - Diadochokinetic rate
 - Story recall
 - List learning
- Linus Platform eye tracking-based memory assessments
- Linus Platform gait and balance assessment
- Linus Platform lifestyle questionnaire

Linus Platform individual tests will be combined to obtain a Linus overall score (Linus score) to measure cognitive status and its agreement with MMSE and RBANS will be assessed.

Subjects will undergo cognitive testing with both the Linus Platform tests and the reference standard RBANS twice, where the second examination will be three to five weeks after the first examination. Test-retest reliability of both individual Linus Platform tests and the combined Linus score will be compared to the test-retest reliability of the RBANS.

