11.2 TEST-RETEST RELIABILITY ANALYSES

Subjects will undergo cognitive testing with both the Linus Platform tests and the reference standard RBANS twice, where the second examination will be three to five weeks after the first examination. Test-retest reliability of both individual Linus Platform tests and the combined Linus score will be compared to the test-retest reliability of the RBANS. For the analysis, subjects who no longer satisfy the inclusion/exclusion criteria prior to the second examination will be excluded.

For, the individual Linus Platform scores, the developed Linus score, and the reference standard RBANS, agreement analyses will be carried out as follows:

- Agreement between the first and second measurements will be measured. A scatter plot of measurement 2 vs. measurement 1 will be generated, superimposed with a line of identity. An unweighted Deming regression (where the variance of the measurement error is determined by the two measurements that were collected 3-5 weeks apart) will be carried out to determine the y-intercept, slope and their two-sided 95% CIs. The ICC will also be determined.
- A hypothesis test of the slope vs. 1 and of the y-intercept vs. 0 will be carried out. Specifically, the following hypothesis test will be carried out: $H_0: \beta_0 = 0$ vs. $H_1: \beta_0 \neq 0$ and $H_0: \beta_1 = 1$ vs. $H_1: \beta_1 \neq 1$ where β_0 and β_1 are the y-intercept and slope, respectively, from the Deming unweighted regression. Each of these will be carried out at a two-sided 0.05 level of significance.

The Evaluable Population will be used for these analyses.

In addition to the above, descriptive statistics (N, mean, standard deviation, median, minimum and maximum) of the Visit 1, Visit 2 and the difference between Visit 1 and Visit 2 (calculated as Visit 1

minus Visit 2) will be presented for the RBANS score, for the Linus total score and for the Linus Platform individual test scores.

Figures will display the above described plots and the associated statistics (y-intercept and slope and their Cis, ICC, estimates of β_0 and β_1 from the Deming regression, and the p-values from the test of the Deming null hypotheses).

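### The pen–tablet Deming regression relies on device-specific error variances that one test per device cannot supply; separately, 10 of the 20 Linus tests have no Visit 1 score for the planned MMSE and test-retest analyses

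*SAP*

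**What the plan says.** **Deming regression.** SAP 9.3 plans an unweighted Deming regression of tablet against pen, for the overall score and the four composite scales, in which the "variance of the measurement error for each of DCTclock-pen and DCTclock-tablet is determined by the two measurements that were collected 3-5 weeks apart". Protocol 10.3.2 has the same text ("An unweighted Deming regression (where the variance of the measurement error for each of DCTclock-pen and DCTclock-tablet is determined"). On the design, Protocol 4.1 states: "Group 1 receives DCTclock-pen at the first visit, with the DCTclock-tablet given at the second visit"; Group 2 has the reverse order. Protocol 7.3.2 lists for the second visit: "Alternate version of DCTclock from visit 1". SAP 11.2 uses similar wording for test-retest: "An unweighted Deming regression (where the variance of the measurement error is determined by the two measurements that were collected 3-5 weeks apart".

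**Linus tests.** SAP 3.2.3 promises: "Linus Platform individual tests will be compared to Mini-Mental State Exam (MMSE) and Repeatable Battery for the Assessment of Neuropsychological Status (RBANS"), and then lists the tests. SAP 11.1 says most of them are given twice. It pairs the MMSE, which is given only at Visit 1, with Visit 1 Linus scores alone. The footnotes to Protocol 7.3.4 read: "PHQ-9 depression screen is included in the decision making and reaction time assessments on visit 2 only" and, after noting that list learning alone is given at Visit 1, "All speech and voice assessments are given on visit 2". The same table marks eye tracking and the lifestyle questionnaire at Visit 2 only.

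**The concern.** Deming regression allows for error in both variables, and its slope depends on the ratio of the two error variances. The usual source for that ratio is repeat measurement on each device. Here the two measurements 3–5 weeks apart come from different devices, so they are not repeats of either. The report would present the slope, intercept and CIs as resting on measured error variances when they rest on an unstated assumption. If the assumption is wrong, the slope is biased and its CI misses the truth too often.

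The second matter is one of scheduling. A test with no Visit 1 score cannot be compared with a Visit 1 MMSE under SAP 11.1 and has no test-retest reliability. If such tests enter the Linus score, that score cannot be computed at Visit 1 either, yet SAP 11.1 and 11.2 use it there.

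**Working it through.** **1. Can the variances be estimated?** The plan gives no figure for this analysis. Its one sample-size figure, 41 for the primary test, reproduces (power 0.902 by the noncentral-t approximation) but has no bearing here.

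One pen–tablet pair per subject yields five moments: two means, two variances and one covariance. The model has six parameters: mean and variance of the true score, intercept, slope and two error variances. It is one short. Random order adds no repeat on either device.

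Illustration: SD of differences 7 (SAP 4), assumed between-subject SD 15, one fixed covariance matrix (both variances 15² + 49/2 = 249.5, covariance 225). Tablet-to-pen ratios of 1/3, 1 and 3 fit it equally well and give slopes of 1.055, 1.000 and 0.948. The data cannot choose between them.

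Treating the pair as a repeat does not help. At the anticipated mean difference of 10, Σd²/(2N) is about (49 + 100)/2 = 74.5 for both devices, against an average error variance of 49/2 = 24.5, because the device difference is absorbed. It also forces the ratio to 1.

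**2. What if ratio 1 is used and is wrong?** From the documents: SD of differences 7, N = 175. Assumed: between-subject SD 10–20, true ratio r from 1/3 to 3, normal errors, true slope 1.

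- Error variances: pen 49/(1 + r), tablet 49r/(1 + r). At r = 3 these are 12.25 and 36.75, so d = tablet − pen = 24.5.
- Slope fitted with ratio 1: b = [d + √(d² + 4T²)]/(2T), where T is the between-subject variance. At SD 15 and r = 3: [24.5 + √(600.25 + 202,500)]/450 = 1.056.
- Coverage: 4,000 simulated trials per setting, jackknife 95% CI.

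| True ratio | SD 10: slope, coverage | SD 15: slope, coverage | SD 20: slope, coverage |
|---|---|---|---|
| 3 | 1.130, 46% | 1.056, 71% | 1.031, 80% |
| 2 | 1.085, 74% | 1.037, 85% | 1.021, 90% |
| 1/2 | 0.922, 66% | 0.964, 81% | 0.980, 87% |
| 1/3 | 0.885, 38% | 0.947, 65% | 0.970, 78% |

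With the true ratio used, coverage is 94–96% throughout. The mean CI half-width when ratio 1 is correct is 0.112, 0.072 and 0.054 for SD 10, 15 and 20, so the bias at ratio 3 ranges from just over half a half-width (0.031 against 0.054) to more than one (0.130 against 0.112). The intercept moves with the slope, by −(b − 1) × mean pen score; the documents do not give that mean.

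**3. Linus tests: SAP 3.2.3 list against the Protocol 7.3.4 schedule.**

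| Group | Listed | Both visits | Visit 2 only |
|---|---|---|---|
| Drawing | 5 | 5 | 0 |
| Reaction time and Go/No-go | 3 | 3 | 0 |
| PHQ-9 | 1 | 0 | 1 |
| Speech | 8 | 1 (list learning) | 7 |
| Eye tracking | 1 | 0 | 1 |
| Gait and balance | 1 | 1 | 0 |
| Lifestyle | 1 | 0 | 1 |
| **Total** | **20** | **10** | **10** |

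Exactly half are given twice. Comparisons 1 and 2 of SAP 11.1 are impossible for the other ten; comparison 3, RBANS at Visit 2, still covers them.

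In Appendix A the descriptive shell marks eye tracking and lifestyle N/A at Visit 1, and the test-retest shell omits them. PHQ-9 and the seven speech tasks are not handled. They have open Visit 1 cells in the first shell and rows in the second, where 8 of 5 + 4 + 8 + 1 = 18 Linus test rows cannot be filled.

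**The case against.** The facts are not in dispute; the case on the other side is about weight.

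- *The wording, taken literally, gives both devices the same variance, hence ratio 1, which is also the main analysis proposed below.* This stands. The defect is an assumption described as a measurement, with no sensitivity analysis, rather than a wrong number.
- *No hypothesis, margin or success rule attaches to the pen–tablet slope or intercept.* This stands, and it limits the consequence.
- *The largest effects need a threefold ratio and a small between-subject SD, neither supported by the documents.* This stands as to size. Both versions are the same clock test, and ordinary fluctuation over 3–5 weeks enters both errors and pulls the ratio towards 1. At SD 15, ratios of 1.25 and 0.8 give slopes of 1.01 and 0.99 with coverage of 93–94%; ratios of 1.5 and 0.67 give coverage of about 92% and 89–90%. But the trial cannot show where the ratio lies.
- *With the slope fixed at 1, both error variances are recoverable.* True, but the slope is what this analysis estimates.
- *SAP 11.2 also needs equal variances, at its two visits.* True. There the pair is at least a repeat of one instrument; across two instruments, equality is part of what is in question.
- *On the Linus tests:* four of the six Linus rows in Protocol 7.3.4 are marked at both visits; the protocol says speech assessments may include the listed tasks; the score is still to be developed; and empty rows would simply stay empty. These points soften the matter. They do not supply the promised MMSE comparison or say what a Visit 1 Linus score contains.

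**Conclusion.** Both parts hold and should be fixed. With a free slope, the device-specific error variances and their ratio cannot be obtained from this design, so the plan's description of its Deming regression is wrong as written. Across the assumed range (between-subject SD 10–20, true ratio 1/3 to 3, true slope 1), using ratio 1 gives slopes of 0.88 to 1.13. Coverage is 38–80% at the threefold extremes and 66–90% at twofold; close to ratio 1 the effect is small. Only the SD of 7 and N = 175 come from the documents.

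The scheduling count rests on the documents alone: 10 of 20 listed tests lack a Visit 1 score and so lose the MMSE comparison, and 8 of 18 test-retest rows cannot be filled. Only secondary and exploratory analyses are affected.

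**What to change.** - **SAP 9.3 and Protocol 10.3.2:** replace the parenthesis with a statement that the tablet-to-pen error-variance ratio cannot be estimated, because each subject takes each device once, and is assumed to be 1. Report slope, intercept and 95% CIs at ratios 1/3, 1/2, 2 and 3 as sensitivity analyses.
- **SAP 11.1:** limit comparisons 1 and 2 to tests given at Visit 1. Add a fourth comparison, MMSE at Visit 1 against the ten Visit-2-only tests, noting the 3–5 week gap.
- **SAP 11.2 and its shell:** limit to tests given at both visits and delete the eight rows that cannot be filled.
- **Descriptive shell:** mark PHQ-9 and the seven speech tasks N/A at Visit 1.
- **Linus score:** state which tests enter it. Any version used at Visit 1 or in test-retest should be built from the same tests at both visits; a fuller Visit 2 score can still serve comparison 3.

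The cost is text and shell edits plus four extra Deming fits for each of five scores (20 fits), with no new data. The added MMSE comparison pairs scores taken weeks apart and must be read that way. If the Linus score includes Visit-2-only tests, a second version from the twice-given tests is needed.

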10 SAFETY ANALYSES

All safety analyses will be performed on the Safety Population.

10.1 PRIMARY SAFETY VARIABLE

The study's primary safety endpoint is the incidence of subjects with serious device-related adverse events from enrollment to completion of the study. Safety will be analyzed on the Safety Population.

A table of treatment emergent adverse events (TEAEs), which are events that started or worsened during or after the first DCTclock or Linus Platform test, will be created. This table will present the number of TEAEs and the number and percent of subjects with at least one TEAE in each visit category (visit 1, between visits, visit 2, or at any time) with which the TEAE is associated.

TEAES will be categorized as follows at each visit, with the number of TEAEs and number and percent of subjects with at least one TEAE presented for each category at each visit:

- Any TEAE,
- TEAE by severity (mild/moderate/severe; if a subject has more than one TEAE, then only the events in the most severe category experienced will be tabulated, and the subject will be placed in the most severe category experienced),
- Relationship (not related or related, where related is further broken down by the categories of possible, probable, definite) to each of the following (if a subject has more than one TEAE, then only the events in the most related category experienced will be tabulated, and the subject will be placed in the most related category experienced):
 - DCTclock-pen (the denominator at Visit 1 and between visits will be those subjects who underwent testing with the pen at Visit 1; the denominator at Visit 2 will be those subjects who underwent testing with the pen at Visit 2)
 - DCTclock-tablet/drawing tests,
 - Decision making/reaction time,
 - Balance/walking,
 - PHQ-9/Lifestyle questionnaire (Visit 2 only),
 - Speech elicitation assessments,
 - Eye tracking assessments (Visit 2 only),
 - Other study assessments,
 - Concomitant medication,
 - Intercurrent intervention/procedure,
 - Pre-existing condition/underlying disease,
 - Intercurrent condition,
 - Incidental finding,
 - Unknown,
 - Other.
- Whether the TEAE led to study discontinuation or not,
- Whether the TEAE is a serious adverse event (SAE or not),
- Whether the TEAE led to death or not.

TEAEs will also be presented in a listing. This listing will include the randomization group, site, subject ID, visit number, date of visit, date of TEAE onset, study day number of onset, date TEAE resolved, number of study days from start to resolution of TEAE, whether it is an SAE or not (if so the reasons for the SAE will be listed after 'Y' in the SAE column), whether or not the study resulted in study discontinuation, outcome, severity, relationship to any study device/test component (any instance in which the TEAE is at least possibly related will be listed and in parentheses will be the exact noted relationship i.e. balance/walking (probable)) and action taken (in any instance in which

the action taken requires a specification, the specification will be written in parentheses i.e. medication (Ativan)).

A listing for device observations (observations associated with the Linus Platform devices) will be presented. This listing will display the randomization group, site, subject ID, description of the observation, observation #, date and study day of observation, whether or not the observation is related to an AE, whether or not the observation is related to Linus platform device components (and if so, which one(s)), time the observation occurred, type of observation, action taken to address the observation/outcome.

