	Number of Events	Number of Subjects with Event [% (n/N)]	Number of Events	Number of Subjects with Event [% (n/N)]	Number of Events	Number of Subjects with Event [% (n/N)]	Number of Events	Number of Subjects with Event [% (n/N)]
Any TEAE								
Severity*								
Mild								
Moderate								
Severe								
Resulted in Study Discontinuation								
Yes								
No								
SAE								
Yes								
No								
Led to Death								
Yes								
No								
Relationship**								
DCTclock-pen								
Not Related								
Related								
Possible								
Probable								
Definite								
DCTclock-tablet/drawing tests								
Not Related								
Related								
Possible								
Probable								
Definite								
Decision making/reaction time								
Not Related								
Related								
Possible								
Probable								
Definite								
Balance/walking								
Not Related								
Related								
Possible								
Probable								
Definite								
PHQ-9/Lifestyle questionnaire								
Not Related								
Related								
Possible								
Probable								
Definite								
Speech elicitation assessments								
Not Related								
Related								
Possible								
Probable								
Definite								

Eye tracking assessments								
Not Related								
Related								
Possible								
Probable								
Definite								
Other study assessments								
Not Related								
Related								
Possible								
Probable								
Definite								
Concomitant medication								
Intercurrent intervention/procedure								
Pre-existing condition/Underlying disease								
Intercurrent condition								
Incidental finding								
Unknown								
Other								

*If a subject has more than one TEAE the events/subject are placed in the most severe category experienced.

**If subject has more than one TEAE, the events/subject are placed into the most related category experienced.

Table #
Treatment Emergent Adverse Events
Safety Population

Randomization Group	Site	Subject ID	Description	Visit Number / Date of Visit	Date of AE Onset/ Study Day Number	Date Resolved / Number of Study Days from Start of AE	SAE	Resulted in Study Discontinuation	Outcome	Severity	Related To	Action Taken
Group XX	XX	XXX-XXX	XXXXXX	XXXXXX XX/XX/XXXX	XX/XX/XXXX	XX/XX/XXXX XX	Y/N	Y/N	XXXXXX	XXXXXX	XXXXXX	XXXX
		XXX-XXX	XXXXXX	XXXXXX XX/XX/XXXX	XX/XX/XXXX	XX/XX/XXXX XX	Y/N	Y/N	XXXXXX	XXXXXX	XXXXXX	XXXX
		XXX-XXX	XXXXXX	XXXXXX XX/XX/XXXX	XX/XX/XXXX	XX/XX/XXXX XX	Y/N	Y/N	XXXXXX	XXXXXX	XXXXXX	XXXX

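### The TEAE table applies the worst-category rule to event counts as well as subject counts, so lesser events drop out of the severity and relationship rows, and the shell footnotes word the rule differently

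*SAP*

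**What the plan says.** SAP section 10.1 sets up a table of treatment-emergent adverse events with two measures in every cell block, "with the number of TEAEs and number and percent of subjects with at least one TEAE presented for each category at each visit". The Appendix A shell has matching separate columns for events and for subjects, under Visit 1, Between Visits, Visit 2 and Total.

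For severity, section 10.1 states two rules for a subject with more than one TEAE. On events, "only the events in the most severe category experienced will be tabulated". On subjects, "the subject will be placed in the most severe category experienced". For relationship to each test component the event rule is parallel: "only the events in the most related category experienced will be tabulated".

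The footnotes to the shell are worded differently. For severity: "If a subject has more than one TEAE the events/subject are placed in the most severe category experienced". For relationship: "the events/subject are placed into the most related category experienced".

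No worst-category rule is attached to the Any TEAE, SAE, death or discontinuation rows. Section 10.1 also says that "TEAEs will also be presented in a listing", with severity and relationship shown for each event. The primary safety endpoint is the "incidence of subjects with serious device-related adverse events from enrollment to completion of the study". SAP section 12, which lists changes from the protocol, does not mention these counting rules.

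**The concern.** Counting each subject once, in the worst category, is the usual convention and avoids double counting people. It has no such purpose for an event count, where each event already has one severity and one relationship grade per component. Under section 10.1 a recorded event can be missing from every row of the severity block, or of a component's relationship block, because the same subject had a worse one. A reader who adds up the rows will not recover the Any TEAE figure and will not be told why.

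The footnotes raise a second problem. Taken at their word they keep the lesser events but re-label them: a mild event becomes severe, or an unrelated event becomes related. Two programmers, one following the text and one following the shell, could produce different tables from the same data.

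The table matters because Aim 2 of the protocol is to characterise the safety profile of the tablet test and the other platform tests. Protocol section 10.3.5 also calls for event numbers alongside subject numbers in the safety reporting.

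**Working it through.** The plan gives no figure on this point, so there is nothing to reproduce. The check has two parts: what each rule does to given data, and how often that would occur.

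**1. The rules on worked cases** (hypothetical subjects; event counts as mild / moderate / severe, then the row sum)

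| Data | Own category | SAP 10.1 text | Footnote, literal |
|---|---|---|---|
| One subject: 2 mild, 1 severe | 2/0/1, sum 3 | 0/0/1, sum 1 | 0/0/3, sum 3 |
| Three subjects: (2 mild, 1 severe), (1 mild, 1 moderate), (1 mild) | 4/1/1, sum 6 | 1/1/1, sum 3 | 1/2/3, sum 6 |
| One subject: 2 mild | 2/0/0, sum 2 | 2/0/0, sum 2 | 2/0/0, sum 2 |

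In the three-subject case the Any TEAE row shows 6 events. The text rule gives severity rows summing to 3. The literal footnote keeps the sum at 6 but shows 3 severe events where there was 1. The subject columns are the same under all three rules: one mild, one moderate, one severe. The third case shows that nothing changes when all of a subject's events share a category.

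The relationship block behaves the same way. A subject with one possible and one definite event loses the possible event under the text. A subject with one unrelated and one probable event has two probable events under the literal footnote.

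**2. Expected size for the severity rows**

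Inputs from the protocol: 37 AEs in 435 participants in the earlier validation study (section 2.3.1) and 200 subjects recruited (section 4.1). Assumed, not in the documents: a 70/25/5 split of mild/moderate/severe, independent of the number of events, and the distribution of events over subjects.

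- Rate per subject: λ = 37/435 = 0.0851. Expected events: 200 × 0.0851 = 17.0.
- Rates by severity: mild 0.0595, moderate 0.0213, severe 0.0043.
- With independent (Poisson) events, the expected number omitted per subject is 0.0595 × (1 − e^(−0.0255)) + 0.0213 × (1 − e^(−0.0043)) = 0.00159. Times 200 this is 0.3 events, or 1.9% of 17.
- The chance that a given subject has events in two or more categories is 0.00154, so the chance that no subject is affected is (1 − 0.00154)^200 = 73%.
- For clustered events (negative binomial, dispersion k, same mean), sum over the number of events n: P(n) × n × [0.70 × (1 − 0.70^(n−1)) + 0.25 × (1 − 0.95^(n−1))] for the omitted events, and P(n) × [1 − 0.70^n − 0.25^n − 0.05^n] for an affected subject.

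| Distribution | Events omitted (of 17.0) | Share | P(subject affected) | P(no subject affected) |
|---|---|---|---|---|
| Poisson | 0.3 | 1.9% | 0.00154 | 73% |
| Negative binomial, k = 0.5 | 0.9 | 5.4% | 0.00393 | 45% |
| Negative binomial, k = 0.2 | 1.7 | 10.0% | 0.00637 | 28% |

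These figures are for the Total column. Within a single visit column the events must also fall in the same period, which is rarer. No comparable estimate was made for the relationship rows, because the documents give no basis for a mix of related and unrelated events.

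**The case against.** The best defence is that little depends on these cells. The primary safety endpoint counts subjects, and subject counts are right under either wording. The Any TEAE, SAE, death and discontinuation rows carry no worst-category rule. With about 17 events expected, the listing lets a reader rebuild the correct table. All of this stands, and it limits the weight of the point.

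The footnotes may also be compressed shorthand for the rule in section 10.1 rather than a second rule. That is possible. It would remove the conflict, but the text rule would still omit events.

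A reader might infer several stronger things that the documents do not support:

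- *That the event totals are wrong.* The Any TEAE total is right under both wordings. Only counts within categories can be wrong, and only the text rule breaks the sum.
- *That severe or definitely related events could be hidden.* Under the text rule those two counts are always exact, because any subject with such an event has it as the worst category. Both wordings shift the displayed mix towards the worse category, so neither flatters the device.
- *That the table is bound to be wrong.* An error needs a subject with TEAEs in two or more categories. On the assumptions above, there is a 28% to 73% chance that no subject's severity counts are affected.
- *That device-relatedness will be misstated to a known degree.* In the earlier study the one SAE and the 36 other AEs were all judged unrelated to the device (protocol section 2.3.1). If that recurred, the relationship rule would change nothing.

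**Conclusion.** The point holds as a specification defect of modest consequence. SAP section 10.1 asks for event counts by category and then excludes some events from them, so the severity and relationship rows need not sum to Any TEAE. The footnotes, read literally, do something else: they keep the sum and inflate the worst category. No passage says which wording governs.

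The expected effect on the severity rows is about 0.3 to 1.7 events out of about 17. This rests on the earlier study's event rate carrying over to 200 subjects, an assumed 70/25/5 severity mix, and event distributions from Poisson to negative binomial with k = 0.2. The effect on the relationship rows is unquantified. The primary safety endpoint, the subject counts and the listing are not touched. The correction is worth making because a planned safety table should agree with itself and with its own shell.

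**What to change.** In SAP section 10.1, state that in the event columns every TEAE is counted once in its own severity category and, for each test component, once in its own relationship category. State that the worst-category rule applies to the subject columns only. Reword both Appendix A footnotes to say the same. The severity rows, and the not-related and related rows for each component, should then sum to the Any TEAE event count, which gives the programmer a simple check.

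The cost is a few lines of SAP and shell wording. No data collection, sample size or endpoint changes.
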